**Primary Endpoint; Part A:**

- The CD34+ cells/kg apheresis yield with 1 apheresis session after MGTA-145 + plerixafor dosing will be presented at each dose of MGTA-145 evaluated. A mean yield and 95% confidence interval (CI) will be presented.
- The number and percentage of subjects with administration-related toxicities and TEAEs will be summarized.

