**Primary Endpoint; Part B:**

- The total CD34+ cells/kg apheresis yield after 2 consecutive days of MGTA-145 + plerixafor mobilization and apheresis collection will be presented. A mean yield and 95% CI will be presented.
- The number and percentage of subjects with administration-related toxicities and TEAEs will be summarized.

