**Table 7: Schedule of Assessments: Part B (Single Dose on 2 Consecutive Days)**

Study Period Procedures	Screening	Baseline	Mobilization/Apheresis b		1-week follow-up (Day 8 to 11) c	End of Study (Day 30) c
	Day -30 to -2	Day -1	Day 1 Part B	Day 2 Part B only		
Informed consent	X					
Medical history	X	X				
Inclusion/exclusion criteria review	X					
Height		X				
Weight		X			X	
Physical examination	X	X			X	
Symptom-directed physical examination			X	X		
Vital signs a	X	X	X	X	X	
Serology d	X					
Serum or urine $\beta$ -hCG (females)	X	X				
12-lead ECG	X					
Urinalysis		X	X	X	X	
Chemistry e	X	X	X	X	X	
Hematology f	X	X	X	X	X	
Anti-drug antibodies		X			X	
Plerixafor administration			X	X		
MGTA-145 administration g			X	X		
Apheresis procedure			X	X		
Apheresis yield h			X	X		
PROMIS and ASCQ-questionnaires i			X		X	
Non-serious AEs and SAEs j	X	X	X	X	X	X k
Concomitant medications	X	X	X	X	X	X k

AE=adverse event; ASCQ-Me=Adult Sickle Cell Quality of Life Measurement Information; BPI=Brief Pain Inventory;  $\beta$ -hCG=beta-human chorionic gonadotropin; CFU= colony-forming unit; ECG=electrocardiogram; PK=pharmacokinetics; NRS=Numeric Rating Scale; SAE=serious adverse event

a Vital sign measurements will be taken in the sitting position after the subject has been resting for 5 minutes. Vital signs should be taken before any blood samples are drawn.

b For Part B, mobilization/collection will occur on 2 consecutive days.

c If a subject does not complete dosing, there will not be follow-up visits. If a subject received MGTA-145 but did not complete apheresis, then follow-up visits are required.

d All subjects enrolled in Part B will be screened for human immunodeficiency virus (HIV), hepatitis B surface antigen (HBsAg), human T-cell leukemia virus (HTLV), and hepatitis C virus (HCV) at the screening visit. Subjects who are HCV antibody positive must have a HCV ribonucleic acid (RNA) polymerase chain reaction (PCR) test.

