e Clinical chemistry consists of sodium, potassium, chloride, bicarbonate, blood urea nitrogen, creatinine, glucose, calcium, aspartate aminotransferase (AST), alanine aminotransferase (ALT), alkaline phosphatase, albumin, total and indirect bilirubin. Clinical chemistry sample collection should be done prior to dosing on Day 1 and Day2. All other clinical chemistry sample collections will be done on the morning of the assessment day.

f Hematology is complete blood count (CBC) with platelets and leukocyte differential. Hematology assessments will be done on the morning of the assessment day.

g MGTA-145 is to be administered via a 3 to 10-minute IV infusion, approximately 2 hours after plerixafor SC injection. Instructions regarding administration are provided in the Study Pharmacy Manual.

h Total nucleated cell count and CD34+ cell count in absolute numbers and per kg.

i ASCQ-Me® and PROMIS® questionnaires will be completed prior to dosing on Day 1.

j Collection of non-serious AEs and SAEs will begin once the Informed Consent Form (ICF) has been signed. Any SAE occurring after the reporting period must be promptly reported if a causal relationship to study drugs is suspected.

k End-of-study visit phone call will occur 30 days ( $\pm$ 3 days) after the last dose of MGTA-145 was received, to assess adverse events and concomitant medications.

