## 6.3. Methodology

Approximately 10 to 14 patients with SCD are planned to be enrolled in this 2-part study. Part A evaluates single-day mobilization and apheresis in 2 sequential patient cohorts, then Part B evaluates two-day mobilization and apheresis in a single patient cohort, following administration of single and 2 consecutive-day doses of MGTA-145 and plerixafor, respectively.

**Part A and Cohort Review Committee assessment:** Part A has a planned enrollment of approximately 7 to 11 evaluable subjects. The first cohort of 4 subjects is to receive a single

0.24 mg/kg SC dose of plerixafor followed 2 hours later by a single 0.03 mg/kg IV dose of MGTA-145. Apheresis is planned to commence within approximately 30 to 45 minutes of dosing. For this initial cohort, only one subject will be dosed and apheresed on a single-day, and each subject will complete the 1-week follow-up visit before a subsequent subject can be dosed.

After the first cohort has completed the 1-week follow-up visit, an independent Data Monitoring Committee (DMC), comprising 3 members with medical expertise in the conduct of stem cell transplantation in patients with SCD as well as the conduct of clinical trials in general, will evaluate the safety, PK, and mobilization kinetics of MGTA-145 before the second cohort may be enrolled. The DMC may recommend enrolling an additional 3 subjects at the 0.03 mg/kg MGTA-145 dose or an additional 7 subjects at a reduced dose of 0.015 mg/kg MGTA-145 or an alternative but lower dosing regimen for this cohort. The MGTA-145 dose will not be escalated during either Parts A or B.

After the second cohort has completed the 1-week follow-up visit, the DMC will likewise evaluate the safety, PK, and mobilization kinetics of MGTA-145 before subjects may be enrolled into Part B. Criteria for the DMC recommendations regarding cohort progression and dosing regimen will be defined in the DMC Charter.

**Part B:** Part B has a planned enrollment of approximately 3 evaluable subjects. Subjects will receive single doses of MGTA-145 and plerixafor on 2 consecutive days, followed by apheresis on each dosing day. The plerixafor and MGTA-145 doses on each of the 2 consecutive days will be identical to that of the second Part A cohort, unless otherwise recommended by the DMC.

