#### 8.1.2. Dose Cohort Planned for Part B

Part B has a planned enrollment of approximately 3 evaluable subjects. Subjects with SCD, aged 18 to 35 years, will receive single doses of MGTA-145 and plerixafor on 2 consecutive days, followed by apheresis on each dosing day. The dose of MGTA-145 will be identical to that of the second Part A cohort, unless otherwise recommended by the DMC.

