#### 10.2.2. Apheresis Yield

Apheresis cell collection as outlined in the Schedule of Events ([Table 6](#) for Part A and [Table 7](#) for Part B) from all subjects enrolled in Parts A and B will proceed according to standardized procedures and start within an hour after MGTA-145 infusion. All subjects will undergo apheresis collection according to institutional practice, not to exceed a total of 8 hours. Apheresis yield will be measured as the total nucleated cell count and CD34+ cell count in absolute numbers and per kilogram. These determinations will be performed using fluorescent flow cytometry.

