### 12.1. Analysis Sets

Evaluable Analysis Sets: The evaluable analysis set for Part A will include all subjects that have received MGTA-145 and plerixafor and undergone successful apheresis collection. The evaluable analysis set for Part B will include all subjects that have received 2 consecutive doses of MGTA-145 and plerixafor, and successfully completed at least 1 of the 2 apheresis sessions.

The Safety Analysis Set: The safety analysis set will consist of all subjects who are enrolled and received a dose of MGTA-145. Subjects in this analysis set will be used for demographic, baseline characteristics, and safety summaries.

Pharmacokinetics Analysis Set: The PK analysis set will include all subjects with available MGTA-145 PK data and no major protocol deviations with relevant impact on PK data.

Pharmacodynamics Analysis Set: The PD analysis set will include all subjects with available PD data and no major protocol deviations with relevant impact on PD data.

In general, data will be presented for Parts A and B of the study separately.

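### Does presenting Parts A and B separately wrongly leave the Part B Day 1 yields out of the single-session CD34+ estimate?

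*Protocol*

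**What the plan says.** The Protocol defines two primary efficacy quantities. In the Synopsis, under the Part A primary endpoint, the CD34+ yield per kg from one apheresis session "will be presented at each dose of MGTA-145 evaluated", as a mean with a 95% confidence interval. Under the Part B primary endpoint, the total CD34+ "apheresis yield after 2 consecutive days of MGTA-145 + plerixafor mobilization and apheresis collection will be presented", again as a mean with a 95% interval. Section 12.5 requires 7 evaluable subjects for the first and 3 for the second.

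On presentation, Section 12.1 says: "In general, data will be presented for Parts A and B of the study separately".

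Three other places bear on the same question:
- Section 12.4.1 groups subjects by dose in every analysis, breaks results out by Part only where that applies, and summarises continuous variables by dose and visit.
- The Synopsis (Statistical Methods) provides for both aggregate and by-cohort presentation, as applicable.
- Section 12 hands the detailed description of all planned analyses, including prespecified exploratory ones, to the SAP.

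On the data, Table 7 notes: "For Part B, mobilization/collection will occur on 2 consecutive days". It schedules an apheresis yield on Day 1 and another on Day 2, each recorded as a "cell count in absolute numbers and per kg". Section 6.3 says: "The plerixafor and MGTA-145 doses on each of the 2 consecutive days will be identical to that of the second Part A cohort", subject to a different recommendation from the Data Monitoring Committee (DMC). Section 8.1.2 repeats this for the study drug: "The dose of MGTA-145 will be identical to that of the second Part A cohort, unless otherwise recommended by the DMC".

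**The concern.** A Part B subject's first day looks like a Part A subject's only day. By default the doses of both drugs are those of the second Part A cohort, collection is on the same day, and the eligibility criteria and yield measurement are shared. Up to 3 of 10 first-session yields at one dose would then not inform the single-session mean, in a study where each subject counts. If the second cohort moves to a lower dose, the 0.03 mg/kg estimate rests on only 4 subjects.

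There is also a question of population. The Part B evaluable set in Section 12.1 requires both doses, while Section 11 leaves the second infusion after a vaso-occlusive event to the investigator's discretion. Anyone who took Day 1 yields from that set would be selecting subjects partly on what happened after Day 1. At stake would be precision in the main efficacy result and, if the pooling were done carelessly, a selected sample.

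**Working it through.** **The plan's own figures.** Cohort sizes in Section 6.3: 4 + 3 + 3 = 10 if the dose is kept, and 4 + 7 + 3 = 14 if 7 subjects are enrolled at 0.015 mg/kg. This matches the stated 10 to 14. On either path 7 Part A subjects share the dose carried into Part B (4 + 3, or 7). There is no power calculation to reproduce, because the study is descriptive (Sections 12.4.1 and 12.5).

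**Size of the gain.** The half-width of a 95% t interval for a mean, in SD units, is t(0.975, n−1)/√n. The Protocol gives no SD for yield, so results stay in SD units and assume an equal sample SD.

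| n | Composition | Half-width (SD) | Narrower than n = 7 |
|---|---|---|---|
| 4 | first cohort alone | 1.591 | – |
| 7 | Part A at the shared dose | 0.925 | – |
| 8 | plus 1 from Part B | 0.836 | 9.6% |
| 9 | plus 2 | 0.769 | 16.9% |
| 10 | plus 3 | 0.715 | 22.7% |

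If the second cohort changes dose, the 4 subjects at 0.03 mg/kg gain nothing. If the DMC changes the dose for Part B, nothing can be pooled.

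**What the gain requires.** Let d be the true difference, in SD units, between the Part B Day 1 mean and the Part A mean. The Protocol gives no value for d, so the values below are assumptions.
- Weight of 3 Part B subjects: 3/10 = 0.30, so the pooled mean shifts by 0.30 d.
- Mean squared error of the pooled mean as an estimate of the Part A mean: 1/10 + (0.30 d)². For Part A alone: 1/7.
- Break-even: 1/10 + 0.09 d² = 1/7, so d² = 0.0429/0.09 = 0.476 and d = 0.690. With 2 or 1 added subjects, d = √(1/7 + 1/m) gives 0.802 (m = 2) or 1.069 (m = 1).
- At d = 0.5: √(0.100 + 0.0225) = 0.350, against √(1/7) = 0.378. Pooling is better.
- At d = 1: √(0.100 + 0.090) = 0.436, against 0.378. Pooling is worse.
- In a simulation of 400,000 runs (normal data, 7 + 3 subjects), the pooled 95% interval covered the Part A mean 95.0%, 93.6% and 90.2% of the time at d = 0, 0.5 and 1.

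**Does the text forbid pooling or give a wrong result?** Set side by side, the rules agree. Part A reports the one-session yield by dose and Part B reports the two-day total. Section 12.1 opens with a qualifier and states a default. Because Section 12.4.1 summarises by dose and visit, and Table 7 records yield on each day, a Part B Day 1 summary already fits the existing text. The aggregate wording in the Synopsis leaves room to combine it with Part A. Neither primary estimate changes, whether or not such a table is added.

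**The case for a change.** The strongest case for the concern is that the analysis costs almost nothing. The data are already collected, the Part A result would stay unchanged beside the pooled one, values could be marked by Part, and in an open-label study an estimate specified before the Part B yields are known is worth more than one added later. The arithmetic is right, and it is true that the Protocol nowhere names a pooled first-session mean. As a suggestion to the authors of the SAP, that stands.

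It does not show that the Protocol states or fixes anything badly:
- **Selection through the Part B evaluable set.** This would arise only if that set were used for a Day 1 estimate, which the Protocol does not plan. Requiring both doses suits a two-day total.
- **Using the pharmacodynamic set instead.** This would not count every Day 1 collection, because the set leaves out subjects with major deviations that affect those data. Unlike the Part A evaluable set, it also does not ask for a successful collection. The 7 Part A subjects in a pooled estimate might therefore not be the 7 in the primary one, and the comparison of 7 with 10 assumes that they are.
- **The collection limit in Section 10.2.2.** It reads: "All subjects will undergo apheresis collection according to institutional practice, not to exceed a total of 8 hours". Whether this applies per session or across both Part B days is not spelled out. If it spanned both days, Day 1 sessions would be less comparable with Part A, which weakens the case for pooling.
- **Sections 12.1 and 12.4.1.** The first uses evaluable sets and the second includes anyone given MGTA-145. This is a separate matter of wording and does not bear on whether the Parts may be shown separately.

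**Conclusion.** The concern does not hold. The Protocol consistently ties the single-session yield to Part A and the two-day yield to Part B. Separate presentation is a defensible default for two different regimens, and the surrounding text leaves a pooled supportive table open. Such a table is ordinary SAP content, so its absence from the Protocol is not an omission.

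The possible gain is an interval at most about 23% narrower at the shared dose. It assumes three usable Part B first sessions, a dose left unchanged by the DMC, an equal SD, and a true difference between the Parts below about 0.69 SD. The Protocol gives no figure for the SD or for that difference. The study tests no hypothesis, and the Protocol text links no decision to the width of this interval.

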### 12.2. Subject Demographic and Other Baseline Characteristics

All data for baseline and demographic variables will be listed by subject. Descriptive summary statistics will be provided.

Relevant medical history, current medical conditions, results of laboratory screens, drug tests, and any other relevant information will be listed by subject.

### 12.3. Exposure and Concomitant Medications

MGTA-145 and plerixafor administrations (time of infusion, duration of infusion, and dose) will be summarized.

Concomitant treatments will be listed and summarized.

### 12.4. Analysis of the Primary, Secondary, and Exploratory Endpoints

The endpoints for this study are provided in [Section 5.1](#) and [Section 5.2](#).

#### 12.4.1. Statistical Methods and Analyses

Statistical summaries will be descriptive in nature. All continuous variables will be summarized by dose and visit (as applicable) using descriptive statistics (number of observations [n], mean, median, standard deviation [SD], minimum, and maximum). All categorical variables will be summarized by dose and visit using frequency counts and percentages. Estimated median, 25th and 75th percentiles and standard error of the mean (SEM) from Kaplan-Meier summaries will be presented for all time-to-event variables. Subjects will be grouped by dose in all analyses and results will be presented by Study Part where applicable. Any subject who receives MGTA-145 will be included in the analyses. No formal hypothesis testing will be performed.

#### **12.4.2. Safety**

Safety analyses will include summaries of AEs and SAEs. The number and percentage of subjects reporting any TEAEs will be summarized. Adverse events will be tabulated by system organ class (SOC) and preferred term (PT) according to the Medical Dictionary for Regulatory Activities (MedDRA) and relationship to treatment. AEs leading to study drug discontinuation and SAEs will be listed. Data listing will be provided for all AEs, TEAEs and SAEs.

Changes in vital signs and clinical laboratory parameters will be assessed from baseline.

#### **12.4.3. Pharmacokinetics**

Plasma concentrations of MGTA-145 will be listed and a summary by time point for each dose cohort will be presented using descriptive statistics (n, mean, SD, median, and range).

#### **12.4.4. Pharmacodynamics**

Peripheral blood will be collected at the timepoints specified in the Schedule of Assessments to measure changes in CD34+ and CD34+CD90+CDRA cell counts, as well as various T-cell subtypes, B cells, monocytes, granulocytes, and NK cells. Cell counts will be analyzed using fluorescent flow cytometry.

Changes in cell functionality will be assessed in terms of CFUs using an automated colony-counting device (StemVision™ from Stemcell Technologies) or manually with an inverted microscope.

### **12.5. Sample Size Calculation**

There are no statistical hypotheses in this trial, therefore there is no sample size calculation. To address the objectives assessing proof of concept of mobilizing CD34+ cells after 1 or 2 days of dosing with MGTA-145 and plerixafor, a minimum sample size of 10 evaluable subjects is considered adequate.

Based on the safety profile including 79 subjects dosed with MGTA-145 in Phase 1 study 145-HV-101, 10 evaluable subjects are deemed a minimal number to assess common drug-related safety events.

The AE that is clearly related to MGTA-145 infusion is transient, Grade 1 back pain, which was observed in a majority of volunteers in the Phase 1 study 145-HV-101. With 10 evaluable subjects, there is sufficient subject exposure to assess for this AE.

Subjects enrolled in the study who are discontinued prior to receiving study drug may be replaced.

Additional subject(s) may be enrolled, if necessary, to ensure minimum numbers of evaluable subjects (i.e., subjects without any major protocol deviations affecting the primary endpoint). For the primary endpoint in Part A, 7 evaluable subjects are required; the first and second DMC assessments require 4 and 7 evaluable subjects, respectively. For the primary endpoint in Part B, 3 evaluable subjects are required.

## 13. DATA REVIEW AND DATABASE MANAGEMENT

### 13.1. Study Site Monitoring

Before an investigational site can enter a subject into the study, a representative of Magenta will:

- Determine the adequacy of the facilities.
- Discuss with the Investigator(s) and other personnel their responsibilities with regard to protocol adherence, and the responsibilities of Magenta or its representatives. This will be documented in a Clinical Study Agreement between Magenta and the Investigator.

During the study, a monitor from Magenta or representative will have regular contacts with the investigational site, for the following:

- Provide information and support to the Investigator(s).
- Confirm that facilities remain acceptable.
- Confirm that the investigational team is adhering to the protocol, that data are being accurately recorded in the eCRFs, and that investigational product accountability checks are being performed.
- Perform source data verification. This includes a comparison of the data in the eCRFs with the subject's medical records, and other records relevant to the study. This will require access to all original records for each subject (e.g., clinic charts).
- Record and report any protocol deviations not previously sent to Magenta.
- Confirm that AEs and SAEs have been properly documented on eCRFs and confirm any SAEs have been forwarded to Magenta and those SAEs that met criteria for reporting have been forwarded to the IRB.

The monitor will be available between visits if the Investigator(s) or other staff need information or advice.

### 13.2. Data Collection

Designated Investigator staff will enter the data required by the protocol into the eCRFs using fully validated software that conforms to 21 Code of Federal Regulations (CFR) Part 11 requirements. Designated Investigator site staff will not be given access to the EDC system until they have been trained. Automatic validation programs will check for data discrepancies and, by generating appropriate error messages, allow the data to be confirmed or corrected before transfer of the data to Magenta. The Investigator must certify that the data entered into the eCRFs are complete and accurate. After database lock, the Investigator will receive any of the following: a compact disc read-only memory (CD-ROM), paper copies, or a password protected universal serial bus (USB) drive of the subject data for archiving at the investigational site.

Data not requiring a separate written record will be defined in the Data Management Reference Manual and Assessment Schedule and can be recorded directly on the eCRFs. All other data captured for this study will have an external originating source (either written or electronic) with the eCRF not being considered as source.

### **13.3. Database Management and Quality Control**

All data should be recorded, handled, and stored in a way that allows its accurate reporting, interpretation, and verification.

Magenta or designee will review the data entered into the eCRFs by investigational staff for completeness and accuracy and will instruct the site personnel to make any required corrections or additions. Queries will be sent to the investigational site using an electronic data query. Designated investigational site staff will be required to respond to each query and confirm or correct the data.

Concomitant medications entered into the database will be coded using the World Health Organization (WHO) Drug Reference List, which employs the Anatomical Therapeutic Chemical classification system. Medical history/current medical conditions and AEs will be coded using MedDRA terminology.

The occurrence of any protocol deviations will be determined.

After these actions have been completed and the database has been declared to be complete and accurate, it will be locked, and the treatment codes will be made available for data analysis.

